### 3.0 Inclusion and exclusion criteria:

# We will recruit 180 IPS clients at Thresholds diagnosed with a mental disorder with or without psychotic features into the randomized controlled trial. *Inclusion/exclusion criteria are outlined below:*

Inclusion Criteria: 1) Over 18 years old;

2a) all chronic schizophrenia spectrum disorders, including schizophrenia, schizoaffective disorder, delusional disorder, brief psychotic disorder, schizophreniform disorder, other specified schizophrenia spectrum and related disorder, and unspecified schizophrenia spectrum and related disorders;

2b) all bipolar spectrum disorders beyond bipolar type I and II to include cyclothymia, other specified bipolar and related disorder, and unspecified bipolar and related disorders;

2c) all depressive disorders, including disruptive mood dysregulation disorder, major depressive disorder, persistent depressive disorder, other specified depressive disorder, and unspecified depressive disorder;2d) post traumatic stress disorder

3) fluency in English; 4) at least a 4th grade reading level; 5) enrolled in IPS; 6) active IPS enrollee as indicated by at least 1 contacts with his/her Employment Specialist in the past 30 days; 7) currently unemployed or underemployed; 8) Planning to go on interviews within 4 weeks of enrolling in the study; 9) willing to be video recorded; and 10) willing and able to provide informed consent. We will review each participant's medical record to confirm his/her mental health history.

Exclusion Criteria: 1) documented developmental or learning disability; 2) medical condition that may compromise cognition (e.g., Parkinson's Disease, Alzheimer's Disease, Huntington's Chorea, Moderate or Greater TBI); 3) uncorrected vision or hearing problems; 4) active suicidal ideation within the last 30 days with at least some intent to act, with or without a specific plan; this would be reflected in a score of 4 or 5 on the Suicidal Ideation section of the Columbia Suicide Severity Rating Scale (CSSRS); and 5) a past suicide attempt within the past 30 days that did not include preparatory acts or behavior, but was defined by a potentially self-injurious act committed with at least some wish to die as a result of the act.

We will not include any special populations: adults unable to consent; minors; infants; childrens; teenagers (ages 17 and younger); or prisoners.

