Data Analysis Plan for Aims 1 & 2. In this intent-to-treat study, we will collect data on 160 subjects. The biostatistician will monitor the data for distribution normality and transform abnormally distributed variables if needed. Correction for Multiple Comparisons: To minimize spurious findings, we will adjust the 3 primary tests using a false discovery rate at 0.05 (see below). Covariates: Although randomization should protect against group differences, we will covary for any between-group differences that are observed regarding demographic, cognitive, clinical and vocational history, booster sessions, and the number of completed interviews. Missing Data: We will follow the intent-to-treat principle and in longitudinal analyses we will use multiple imputation models to analyze the data in the presence of missing data. Data processing and cleaning will occur during the study, including checking for missing data and inconsistencies. All videos will be stored on the project's secure server. A Data Safety and Monitoring Board will monitor for adverse events (see 15.0 below).

**Hypothesis 1:** IPS+VR trainees will have higher employment rates than IPS Only by T3. **To test H1**, we will use multiple logistic regression and a Wald Chi-square test of the coefficient to its standard error, to compare the adjusted employment proportions in the two conditions (attained a job=1 vs. failed to attain a job or censored with a job=0, between T1 and T3). We calculated power using simulation in R, correcting for small samples and multiple testing with false discovery rate for the 4 primary tests (our power analysis is conservative, relying on Bonferroni corrections for all tests). Accounting for 10% missing, our trial that recruits 80 subjects in each arm has 80% power for a two-sided 0.05/4=.0125 level test when the OR = 3.2, with IPS+VR effectively doubling the

rate from 25% to 53% employment. Based on our earlier study where we found an OR of 8.7, or effectively tripling the employment rate from 25% to 75%, and a power of 0.99 at this magnitude of effect, we feel confident that we will have sufficient power in this study.

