**Hypothesis 4:** IPS+VR trainees will have greater reductions in psychological distress than IPS Only between T1 and T3. **To test H4**, groups will be contrasted on change via RM-ANOVA with time as a repeated measure and group as the main effect. Power analyses for RM-ANOVA focused on contrasts between T1 and T3. A correlation of r=.5 between T1 and T3 was assumed. Power was estimated for a range of relative effect sizes (d=.2 to d=.8; difference between IPS Only and IPS+VR) for RM-ANOVA time-by-treatment interaction effects. Assuming an overall reduction in distress of d=.5 (across both groups), all relative effect sizes were centered on this average (e.g., a relative difference in d=.8, corresponds to d=.9 for IPS+VR and d=.1 for IPS, averaging out to d=.5 overall). For ANOVA change contrasts of IPS only vs. IPS+VR between T1 and T3, 160 subjects will be sufficient to detect d=.50 (d=.75 vs .25) with 80% power for 0.0125-level test. ANCOVA will test for differences in T3 distress while covarying for T1 distress. Baseline differences (e.g., cognition) will be tested as covariates.

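### Hypothesis 4's stated 80% power is about 74% at the plan's own inputs, and the stronger ANCOVA in the same paragraph has no stated status or power

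*Combined protocol and SAP*

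**What the plan says.** All of this is in section 14.0.

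- **Test.** Under Hypothesis 4, "groups will be contrasted on change via RM-ANOVA with time as a repeated measure and group as the main effect". The power statement concerns the time-by-treatment interaction between T1 and T3.
- **Inputs and claim.** "A correlation of r=.5 between T1 and T3 was assumed". The effect is the between-arm difference in standardised reduction, and "160 subjects will be sufficient to detect d=.50 (d=.75 vs .25) with 80% power for 0.0125-level test".
- **Second analysis.** Near the end of the paragraph: "ANCOVA will test for differences in T3 distress while covarying for T1 distress". No power is given for it, and nothing says how it ranks against the ANOVA.
- **Level and arm size.** Hypothesis 4 gives neither sidedness nor arm size. Hypothesis 1 gives both: "Accounting for 10% missing, our trial that recruits 80 subjects in each arm has 80% power for a two-sided 0.05/4=.0125 level test".
- **Multiplicity.** Hypothesis 1 calls the 0.0125 level conservative, "for the 4 primary tests (our power analysis is conservative, relying on Bonferroni corrections for all tests"; the decision rule announced earlier is that "we will adjust the 3 primary tests using a false discovery rate at 0.05".

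**The concern.** The paragraph supplies every input needed to check its own power figure, and the figure does not follow from them. The overstatement is about 6 percentage points, at the significance level that the plan chose for its power calculations.

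The paragraph also names two analyses of the same outcome. In a randomised comparison, change-score ANOVA and baseline-adjusted ANCOVA estimate the same treatment effect, but they can give different p-values. With the ANCOVA's status undefined, a reader cannot tell which result would settle the hypothesis if they disagreed. The plan also reports power only for the less efficient test: the ANCOVA's error variance is (1+r)/2 times that of the change score, so 25% smaller at r=.5.

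**Working it through.** **Inputs.** From Hypothesis 4: d=.50, r=.5, 160 subjects, level 0.0125, stated power 80%. From Hypothesis 1: two-sided test, 80 per arm. Assumed: equal SD at T1 and T3.

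**Formulas (SD units).**
- SD of change = sqrt(2(1−r)).
- ANCOVA residual SD = sqrt(1−r²), with one error degree of freedom fewer.
- Noncentrality = (d/SD)·sqrt(n/2), with n per arm; power from the noncentral t distribution.

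**Step 1: does this method reproduce the plan elsewhere?** Hypothesis 2 uses d=.42, r=.7 and level .0125, and states a 6.9% reduction in within-subject error and 82% power.
- SD of change = sqrt(0.6) = 0.775, so d/SD = 0.542.
- Error reduction = (0.542²/4)/(1+0.542²/4) = 6.8%.
- Noncentrality = 0.542·sqrt(40) = 3.43, giving two-sided power of 81.5% at 80 per arm.

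Both figures agree. A one-sided test would give 87.7%, and 80 in total (40 per arm) would give 45.2%. So the plan's Hypothesis 2 calculation was two-sided with 80 per arm.

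**Step 2: Hypothesis 4 by ANOVA.** SD of change = sqrt(2·0.5) = 1.0. It equals the raw SD, so it does not matter which SD scales d. Noncentrality = 0.50·sqrt(40) = 3.16. Power = 73.7%. The interaction F test (noncentrality 10) gives the same value, and simulation gives 73.5% to 73.7%. Reaching 80% requires d of about .53, or 91 per arm, or r of about .56, or a level of about 0.022.

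**Step 3: ANCOVA.** Residual SD = sqrt(0.75) = 0.866. Noncentrality = (0.50/0.866)·sqrt(40) = 3.65. Power = 86.8% (simulation 86.0% to 86.5%). The detectable d is about .46, and 69 per arm give 80%.

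**Step 4: variants (two-sided unless marked).**

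| Setting | ANOVA | ANCOVA |
|---|---|---|
| 80 per arm, 0.0125 | 73.7% | 86.8% |
| 80 per arm, 0.0125 one-sided | 81.5% | 91.6% |
| 80 per arm, 0.05/3 | 77.0% | 89.0% |
| 80 per arm, 0.05 | 88.2% | 95.2% |
| 72 per arm (10% loss), 0.0125 | 68.1% | 82.3% |
| 90 per arm, 0.0125 | 79.6% | 91.0% |

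At 80 per arm and 0.0125, r from .3 to .7 gives 56% to 94% for the ANOVA and 78% to 97% for the ANCOVA.

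**Step 5: the planned false-discovery-rate rule.** Simulated with Benjamini-Hochberg at 0.05 and four tests assumed independent, 80 per arm:

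| Hypotheses 1 to 3 | ANOVA | ANCOVA |
|---|---|---|
| All null | 74.3% | 87.2% |
| Only Hypothesis 2 at its stated power | 80.9% | 91.2% |
| All at their stated power | 87.5% | 94.9% |

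**A related slip in Hypothesis 2.** The sentence on a 4.7% error reduction detectable with 80% power names no level. With 160 subjects the noncentrality is 160·0.047/0.953 = 7.9, which gives 79.7% power at 0.05 but 61.2% at 0.0125. A 4.7% reduction corresponds to d=.34; the stated difference of .32 corresponds to 4.1%.

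**The case against.** The best objection is that 0.0125 is not the decision rule. The plan says its power analysis is conservative and that it will control the false discovery rate. Under that rule the ANOVA passes 80% as soon as Hypothesis 2 has its stated power. This stands: the error lies in the quoted 0.0125-level figure and does not by itself show that Hypothesis 4 is underpowered as planned.

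Second, Hypothesis 4 states no sidedness, and a one-sided test would give 81.5%. But Hypothesis 1 defines the level as two-sided, the ANOVA interaction F test has no direction, and the Hypothesis 2 figure reproduces only two-sided.

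Third, section 3.0 gives a larger sample: "We will recruit 180 IPS clients at Thresholds diagnosed with a mental disorder". At 90 per arm the power is 79.6%, which may be where the 80% came from. The sentence nevertheless says 160, and 180 less 10% leaves 162, or 81 per arm, with 74.3%. The 68% figure applies the 10% loss to 160. The plan states that loss only for Hypothesis 1 and intends multiple imputation, so 68% is a conditional result.

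Fourth, the ANOVA is a valid prespecified test and is clearly introduced first, so what the ANCOVA lacks is a label, not a description. That is fair. It is also true that the ANCOVA's power rests on an assumed r: at r=.3 it is 78%. It still exceeds the ANOVA's at every value of r examined.

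**Conclusion.** The concern holds. At Hypothesis 4's own inputs, 160 subjects give the change contrast about 74% power at a two-sided 0.0125 level, not 80%; the detectable effect is about d=.53. The ANCOVA named alongside it has about 87%, and about 82% if 10% are lost, yet has neither a stated status nor a stated power. The result assumes equal SDs at the two times, 80 per arm, and the two-sided level carried over from Hypothesis 1. It shows a wrong planning figure and an unresolved choice between two analyses. It does not show inadequate power under the false-discovery-rate rule, where the answer depends on the other tests.

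**What to change.** Preferred: by a dated amendment, name the ANCOVA already in the text (T3 distress on arm and T1 distress) as the test that decides Hypothesis 4, with the repeated-measures ANOVA supportive. State its power as about 87% for d=.50, r=.5, two-sided 0.0125 and 80 per arm, or about 82% with 10% loss.

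Alternatively, keep the ANOVA as the deciding test, restate its power as about 74% (detectable d about .53), and label the ANCOVA supportive. This corrects the error without changing the test.

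In either case, state the sidedness and name the distress instrument, since the BPRS and the Beck Depression Inventory are both collected at pre-test and at 6 months and neither is designated. In Hypothesis 2, write the sample as 80 per arm and correct the detectable effect to about .34 at 0.05, or about .41 at 0.0125.

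No new data or visits are needed. The constraint is timing: a note dated 1/29/18 in section 4.0 (D.5) shows the trial was already running, so a change of deciding test must be made before whoever chooses it sees results by arm. Section 15.0 has the statistician present preliminary data to the DSMB in closed session; if those were shown by arm, someone else should make the choice.

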Our long-term goals are to develop, evaluate, and implement virtual reality interventions that enhance vocational recovery from SMI. The objectives of this application are to: 1) evaluate if VR enhances SE outcomes and if the benefits of VR generalize to improved social skills and reduced psychological distress; and 2) identify facilitators and barriers associated with large-scale implementation of VR. **Our central hypothesis is that VR will enhance vocational outcomes in a SE program.** This hypothesis is based on our research showing that VR performance predicted greater odds of receiving a job offer and a shorter duration until receiving a job offer, and recommendations from a community advisory board of SE leaders and staff. We also recognize that VR needs research to maximize the effectiveness of VR in real-world settings.

In this application we propose to conduct a single-blinded confirmatory effectiveness RCT (and a process evaluation) of VR by comparing subjects receiving SE with VR (instead of clinician role-plays) (SE+VR) to subjects receiving SE as usual (SE Only). Subjects will include adults with SMI who are newly enrolled in SE at Thresholds, the largest community mental health service provider in Chicago. We are well prepared to conduct this study because our team has extensive experience with community-based vocational and implementation research, and in leading prior studies at Thresholds. The Specific Aims are:

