### 2.0 Background / Literature Review / Rationale for the study:

More than 9 million Americans have severe mental illnesses (e.g., major depression, bipolar disorder, and schizophrenia) with long periods of clinical stability when they can work. A primary aim for adults recovering from SMI is getting a job as 70% of this population wants to work, and employment increases quality of life. Thus, adults with SMI, service providers, and policy makers view a return to work as a critical milestone for recovery. However, only 10-15% of this group is employed and struggling to find jobs increases their psychological distress.

The field's gold standard vocational program for adults with SMI is Supported Employment (SE), which uses staff-based role-plays to train interview skills. However, despite their desire to improve interview skills only 30% of SE clients reported this method was helpful. Also, SE clients were more likely to get a job if SE staff were present during interviews. Thus, SE job interview training methods may be limited, which is a major barrier for this group to get a competitive job offer.

Based on the need to enhance interview skills, NIMH funded the development and evaluation of Virtual Reality Job Interview Training (VR) in a series of RCT efficacy studies (R44 MH080496). Briefly, VR overcomes the limitations of SE interview training by using behavioral learning principles that facilitate sustainable changes in behavior. VR improved interview skills in a lab setting and demonstrated efficacy (increased likelihood of attaining a job offer and getting job offers sooner) for four independent groups of adults with SMI. Moving forward we will evaluate VR in the community at Thresholds, which is the largest SE provider in Chicago and offers a standardized version of SE called *Individual Placement and Support (IPS)*. Although IPS strives for rapid job placement, it devotes much less attention to job interview training, which is a limitation to IPS given that "competitive" jobs require interviews.

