**Hypothesis 5:** IPS+VR will be more cost-effective than IPS Only. To test **H5**, we will conduct a costeffectiveness analysis (CEA) to assess the short-term cost-effectiveness of IPS+VR relative to IPS Only using a societal perspective, which includes intervention costs and client costs provided by the IPS program director. Intervention costs include variable costs (e.g., time spent by ECRs) and fixed costs (e.g., costs supporting hiring, training, and coordination). Client costs will include time using VR and travel costs. We will use standard approaches to identifying and assigning unit costs for each cost component. We will use job attainment rate as our measure of effectiveness. The main step is to calculate an incremental cost-effectiveness ratio (ICER), which is defined as the difference in total costs between the IPS+VR and IPS Only groups, divided by the between-group difference in job attainment rate. Confidence intervals will be calculated around the ICER using bootstrapping and Fieller's theorem. We will conduct sensitivity analysis by deriving cost-effectiveness acceptability curves that display the probability of IPS+VR being cost-effective at various threshold values. **Exploratory (Person-Level):** To study the generalizability of VR to social skills, we will evaluate if more VR training (i.e., number of trials) is associated with a longer job tenure (number of weeks) and enhanced social skills using linear regression; covariates will include demographic, cognitive, vocational, and training characteristics that differentiate groups. **Exploratory (System-Level):** We will explore if, as a result of VR, ESPs reallocate their interviewing hours towards building larger employer networks, completing more job applications with clients, and engaging in more hours of coaching work communication with clients.

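### H5 calls its cost-effectiveness ratio societal, but it assigns only programme and client costs, and the only client time it names is time on VR

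*Combined protocol and SAP*

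**What the plan says.** Section 14.0, Hypothesis 5, describes the analysis as "using a societal perspective, which includes intervention costs and client costs provided by the IPS program director". It then gives the components. On the programme side: "Intervention costs include variable costs (e.g., time spent by ECRs) and fixed costs (e.g., costs supporting hiring, training, and coordination". On the client side: "Client costs will include time using VR and travel costs". The ratio is "the difference in total costs between the IPS+VR and IPS Only groups, divided by the between-group difference in job attainment rate".

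The comparator also contains interview training. Section 1.0 sets out the trial "by comparing subjects receiving SE with VR (instead of clinician role-plays", and section 2.0 describes Supported Employment as the programme "which uses staff-based role-plays to train interview skills". Section 4.0, D.5, gives IPS Only clients no VR through study resources; they may use it within regular services after the 9-month call.

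**The concern.** There are two separate problems.

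First, the label is wider than the costs. A reader of a societal ratio expects costs that fall outside the programme and the client, and none is assigned. If H5 is reported as societal, agencies deciding on adoption, whom section 2.0 names as the audience, would take it for something it is not.

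Second, the client-time term as named can only be non-zero in one arm. VR is a substitute for staff-led practice, and that practice also takes clients' time. The plan treats the displaced staff hours as a resource worth tracking but names no matching client hours. Because the numerator is a difference in total costs, an item counted in one arm passes straight into the ratio.

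**Working it through.** H5 states no cost, ratio or power figure, so there is nothing of the plan's own to reproduce. The check has two parts.

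**Part 1: perspective against data sources**

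- *Health-service use.* The post-test, 6-month and 9-month measures (section 4.0, D.6, D.8, D.10) are symptom, substance-use, quality-of-life, health-status, motivation, anxiety, self-efficacy and technology-comfort scales, role-plays, a training-experience questionnaire and an employment interview. None is described as recording service use. The SCID gives past psychiatric hospitalisations at baseline (D.2) but is not listed again. The health record is used for prescreening (D.1) and for participants who cannot be reached (scheduling steps after D.8); no extraction for costing is described.
- *Earnings.* Hours worked and hourly wage are collected at follow-up (D.8, D.10), but H5 does not say whether they enter.
- *Staff logs.* These hold staff hours, are anonymous to the study team, and have no described link to client or arm (section 4.0, E.3, Level 5). They do not supply client time by arm.
- *Budget impact analysis.* This takes the implementing organisation's view (section 14.0, Aim 3), so it does not widen the perspective.

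**Part 2: size of the client-time term**

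Client-time term per additional job = (VR hours − IPS Only practice hours) × value of an hour ÷ difference in job attainment rate.

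Inputs:

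- VR hours: up to 10 (section 4.0, B and F.1), or 6 × 2 = 12 (section 4.0, D.5). Both are carried, because the documents disagree.
- Value of an hour: $10 to $20. **Assumption**; the documents give none.
- Difference under H1: 0.53 − 0.25 = 0.28.
- Difference under H3: the control proportion is 0.20 by T3 and the hazard ratio is 2.0. With a constant hazard the VR proportion is 1 − 0.80² = 0.36, so the difference is 0.36 − 0.20 = 0.16.
- Travel: left out, since H5 ties it to neither arm.

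With IPS Only practice hours at zero, the cost per VR client runs from 10 × $10 = $100 to 12 × $20 = $240.

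| Difference | Low end | High end |
|---|---|---|
| 0.28 (H1) | $100 ÷ 0.28 = $357 | $240 ÷ 0.28 = $857 |
| 0.16 (H3) | $100 ÷ 0.16 = $625 | $240 ÷ 0.16 = $1,500 |

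The effect of counting IPS Only practice time, at $15 per hour and a difference of 0.28 (comparator hours are assumed):

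| IPS Only hours | 10 VR hours | 12 VR hours |
|---|---|---|
| 0 | $150 ÷ 0.28 = $536 | $180 ÷ 0.28 = $643 |
| 2 | $120 ÷ 0.28 = $429 | $150 ÷ 0.28 = $536 |
| 5 | $75 ÷ 0.28 = $268 | $105 ÷ 0.28 = $375 |
| 10 | $0 | $30 ÷ 0.28 = $107 |

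The part of the term that comes from the costing rule is the drop from the top row to the row matching true IPS Only practice time.

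**The case against.** The strongest reply is that H5 is under-specified, not wrong. Both cost lists are worded as inclusions, the numerator is total cost in each arm, and standard costing approaches are cited. A reader might infer that IPS Only client time is excluded. The documents do not say so; it is unnamed. That stands, and it limits the point to what happens if the text is followed as written. It does not remove the point, because an analyst could not tell from H5 which IPS Only hours to count or where to find them.

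Several other strong readings also go too far:

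- *The correct client-time increment is zero.* That needs equal practice time in both arms. Section 2.0 says IPS gives interview training much less attention, which suggests comparator time is small and most VR time is a real increment.
- *VR travel should be added to the imbalance.* H5 does not confine travel to one arm. The $10 payment in D.5 goes only to those who had to travel, and home use is allowed.
- *Justice costs cannot enter.* The Employment History Interview covers criminal justice history at baseline (D.3) and is repeated in a follow-up version. The form is not shown, so absence at follow-up is unproven.
- *Home VR time has no source.* VR use after the first month is monitored by ID number (F.1). Whether the programme director supplies quantities, unit costs or both is unclear.
- *H5 could be made falsely favourable.* One-sided client time raises the cost of the VR arm, so it works against H5. The direction of the other omissions cannot be determined.

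**Conclusion.** The concern holds in a limited form. H5 claims a societal perspective but assigns only programme and client costs. Its single named client-time item is zero in IPS Only by design, while client time in the role-plays being replaced is left unstated. Taken literally, the client-time term is about $357 to $857 per additional job at a difference of 0.28, or $625 to $1,500 at 0.16. These figures rest on the assumed $10 to $20 per hour, on 10 to 12 VR hours, on no comparator time and on no travel. They are the whole term, not the bias; the bias is the part that IPS Only practice time would offset, and it may be small. With no total cost or threshold in the plan, materiality for the final decision cannot be judged. This should be corrected because the label determines how H5 is read and the correction is cheap. It does not touch H1 to H4.

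**What to change.** In section 14.0, Hypothesis 5:

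1. Restate the perspective as programme and participant, and limit H5's conclusion to it. State that wages are not netted from costs, because job attainment is already the measure of effect.
2. Apply one client-cost rule to both arms: hours and trips for interview preparation, whether VR or staff-led, at the same unit costs.
3. Take VR hours from the monitored VR use. Take other hours from one item added to the Employment History Interview already given at the post-test visit (section 4.0, D.6), asking about the period since the baseline visits. The monthly calls are not suitable, because they start after post-test (D.7) and ask about the past month, so they would miss IPS Only practice in the training window. If later as-needed VR use is also costed, ask the item again at the 6-month visit, where the interview is repeated.
4. Report a sensitivity analysis with client time excluded in both arms. It needs no new data and covers participants already past post-test; D.5 shows that the study was running by January 2018.
5. Reconcile the two statements of VR exposure (section 4.0, B and F.1 against D.5) before VR time is costed.

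The cost is plan wording and one interview item. The downsides are a narrower stated perspective, some recall error in client hours, and missing data for participants enrolled before the item is added.
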